10.6 Subject Completion/Discontinuation

A subject is considered to have completed the study when he/she ceases active participation in the study because the subject has, or is presumed to have, completed all study procedures according with the protocol (with or without protocol deviations).

Reasons for completion/discontinuation will be reported on the Completion/Discontinuation eCRF, including:

- Completed
- Screen failure
- AE (eg, death),
- Discontinuation by subject (eg, lost to follow-up [defined as 3 documented unsuccessful attempts to contact the subject], dropout)

- Physician decision (eg, pregnancy)
- Progressive disease
- Non-compliance with IP/protocol deviation(s), recovery, study terminated by sponsor
- Other (reason to be specified by the investigator, eg, technical problems)

Regardless of the reason, all data available for the subject up to the time of completion/discontinuation should be recorded on the appropriate eCRF.

Every effort will be made to have discontinued subjects complete the study completion/termination visit. If the completion/termination visit is done as an additional, unscheduled visit, the assessment results shall be recorded with the completion/termination visit. If a subject terminates participation in the study and does not return for the completion/termination visit, their last recorded assessments shall remain recorded with their last visit. The reason for discontinuation will be recorded, and the data collected up to the time of discontinuation will be used in the analysis and included in the clinical study report.

If additional assessments are required, the assessments shall be recorded separately. Assessments to be done at the termination visit (including in cases of withdraw or discontinuation) can be found in [Table 1](#) and [Table 2](#).

After the discontinuation visit, if the subject agrees, a follow-up visit performing the same assessments as the Week 52 visit should be conducted 5 weeks after last IP dose.

In the event of subject discontinuation due to an AE, clinical and/or laboratory investigations that are beyond the scope of the required study observations/assessments may be done as part of the evaluation of the event. These investigations will take place under the direction of the investigator in consultation with the sponsor, and the details of the outcome may be reported to the appropriate regulatory authorities by the sponsor.

10.7 Procedures for Monitoring Subject Compliance

Subject compliance with the treatment regimen will be monitored by completion of a subject diary detailing the time and date of self-administration/home treatment of M923 or EU RPP.

Subjects receiving less than 18 doses (75% compliance) will be considered non-compliant

11. ASSESSMENT OF EFFICACY, IMMUNOGENICITY, AND PHARMACOKINETICS

11.1 Primary Efficacy Assessment

The primary efficacy outcome measure is the proportion of subjects treated with M923 vs EU RPP who achieve a 75% reduction in PASI from Week 0 (baseline) to Week 16 of the treatment period. Psoriasis will be assessed using the PASI, which is a measure of the average redness, thickness, and scaliness of the lesions (each graded on a 0 to 4 scale, weighed by the area of involvement. PASI score will be recorded by the investigator/site staff at clinic visits as shown in the schedule in [Table 1](#).

11.2 Secondary Efficacy Assessments

Secondary efficacy outcome measures consisting of response as measured by the sPGA, PASI scores over time, and health-related quality of life by the DLQI and the EQ-5D-5L will be evaluated in subjects treated with M923 vs EU RPP as detailed in [Section 11.2.1](#), [Section 11.2.2](#), and [Section 11.2.4](#).

11.2.1 Static Physician Global Assessment

The proportion of subjects with response by sPGA of clear or almost clear (6-point scale) at Week 16 in subjects treated with M923 vs EU RPP treatment will be assessed. In addition, the sPGA response rate of subjects treated with M923 vs EU RPP over time will be compared.

The sPGA will be evaluated by a qualified investigator at the site. The sPGA is the physician's determination of the subject's psoriasis lesions overall at a given time point. The sPGA is recommended as an endpoint to use to assess efficacy in the treatment of psoriasis.⁵ Overall lesions are categorized by descriptions for induration, erythema, and scaling. For the analysis of responses, the subject's psoriasis is assessed at a given time point on a 6 point scale in which 0 = cleared, 1 = minimal, 2 = mild, 3 = moderate, 4 = severe, 5 = very severe. The sPGA evaluations will be recorded on the eCRF by the investigator/site staff at clinic visits as shown in the schedule in [Table 1](#).

11.2.2 Psoriasis Area and Severity Index

A comparison of the proportion of subjects treated with M923 vs EU RPP who achieve 50%, 75%, and 90% reductions in psoriasis severity over time, as well as the response of subjects treated with M923 and EU RPP over time based on the absolute PASI score, will be assessed.

The PASI will be evaluated by a qualified investigator at the site. The PASI combines assessments of the extent of body-surface involvement in 4 anatomical regions (head [10% of BSA], arms [20% of BSA], trunk [30% of BSA], and legs [40% of BSA]) and the severity of desquamation (scaling), erythema (redness), and induration (thickness) in each region, yielding an overall score of 0 for no disease to 72 for the most severe disease.⁶ Each of the body areas is scored by itself, and then the four scores are combined into the final PASI. For each body area, the percent of area of skin involved is estimated and then transformed into a score from 0 to 6: 0 = 0% of involved area, 1 = < 10% of involved area, 2 = 10% to 29% of involved area, 3 = 30% to 49% of involved area, 4 = 50% to 69% of involved area, 5 = 70% to 89% of involved area, 6 = 90% to 100% of involved area. Severity parameters are measured on a five point scale in which 0 = None, 1 = Slight, 2 = Moderate, 3 = Severe, 4 = Very Severe. The sum of all 3 severity parameters is then calculated for each body area, multiplied by the area score for that area and multiplied by weight of respective section (0.1 for head, 0.2 for arms, 0.3 for trunk and 0.4 for legs). Subjects achieving PASI 50, 75, 90, or 100 are defined as having an improvement of at least 50%, 75%, 90%, or 100%, respectively, in the PASI compared with baseline. Information required to calculate the PASI will be recorded on the eCRF by the investigator/site staff at clinic visits as shown in the schedule in [Table 1](#).

11.2.3 Body Surface Area

The investigator will evaluate the percentage involvement of psoriasis on each subject's BSA on a continuous scale from 0% = no involvement to 100% = full involvement, where 1% corresponds to the size of the subject's handprint including the palm, fingers, and thumb.⁷

11.2.4 Patient-reported Outcomes – Dermatology Life Quality Index (DLQI) and EuroQoL 5-Dimension Health Status Questionnaire

Health-related quality of life during treatment with M923 and EU RPP will be evaluated by the DLQI and the EQ-5D-5L questionnaires. The assessments will be recorded on the eCRF by the investigator/site staff at clinic visits as shown in the schedule in [Table 1](#).

11.3 Pharmacokinetics Assessments

Blood samples for analysis of serum M923 or EU RPP in terms of serum levels will be collected at the times shown in the schedule in [Table 1](#). Samples should be obtained prior to administering study drug if an administration occurs at that visit and before any hematology/chemistry samples to be drawn at that visit. Samples will be collected and aliquotted into primary and back-up specimens. Back-up specimens should be stored at -20 °C or -70 °C until shipment. Blood sample processing and handling details will be presented in a separate laboratory manual.

Bioanalysis

Samples for determination of M923 or EU RPP concentrations in serum will be analyzed by Quintiles BioSciences, on behalf of Baxalta US Inc., using appropriate bioanalytical methods, which will be described in a separate bioanalytical report. All samples still within the known stability of the analytes of interest (ie, M923 or EU RPP) at time of receipt by the bioanalytical laboratory will be analyzed.

11.4 Immunogenicity Assessments

Blood samples for analysis of and ADA levels to M923 and EU RPP will be collected at the times shown in the schedule in [Table 1](#). ADA analysis will be conducted using a screening assay based on M923 to identify potentially positive ADA samples.

Subsequently, confirmatory assays based on EU RPP and M923 will be used to confirm the positive status of samples. In confirmed positive samples, a third assay will be used to determine the relative titer of the ADA; a subsequent neutralizing antibodies assay will be used to determine the presence of neutralizing and an iso-typing assay will be done. Blood sample processing and handling details will be presented in a separate laboratory manual. Serum samples will be analyzed by Quintiles BioSciences using validated assays.

12. ASSESSMENT OF SAFETY

12.1 Adverse Events

12.1.1 Definitions

An AE is defined as any untoward medical occurrence in a subject administered an IP that does not necessarily have a causal relationship with the treatment. An AE can therefore be any unfavorable and unintended sign (eg, an abnormal laboratory finding), symptom (eg, rash, pain, discomfort, fever, dizziness, etc.), disease (eg, peritonitis, bacteremia, etc.), or outcome of death temporally associated with the use of an IP, whether or not considered causally related to the IP.

12.1.1.1 Serious Adverse Events

A SAE is defined as an untoward medical occurrence that at any dose meets 1 or more of the following criteria:

- Outcome is fatal/results in death
- Is life-threatening – defined as an event in which the subject was, in the judgment of the investigator, at risk of death at the time of the event; it does not refer to an event that hypothetically might have caused death had it been more severe
- Requires inpatient hospitalization or results in prolongation of an existing hospitalization – inpatient hospitalization refers to any inpatient admission, regardless of length of stay
 - Hospitalizations occurring during the study and planned before subject randomization will not be considered SAEs and should be clearly stated in the subject's medical history
- Results in persistent or significant disability/incapacity (ie, a substantial disruption of a person's ability to conduct normal life functions)
- Is a congenital anomaly/birth defect
- Is a medically important event – a medical event that may not be immediately life-threatening or result in death or require hospitalization but may jeopardize the subject or may require medical or surgical intervention to prevent 1 of the other outcomes listed in the definitions above. Examples of such events are:
 - Intensive treatment in an emergency room or at home for allergic bronchospasm, blood dyscrasias, or convulsions that do not result in hospitalization, or development of drug dependence or drug abuse
 - Reviewed and confirmed seroconversion for HIV, hepatitis A virus, HBV, HCV, hepatitis E virus, or parvovirus B19

12.1.1.2 Non-Serious Adverse Events

A **non-serious** AE is an AE that does not meet the criteria of an SAE.

12.1.1.3 Unexpected Adverse Events

An unexpected AE is an AE whose nature, severity, specificity, or outcome is not consistent with the term, representation, or description used in the Reference Safety Information (eg, IB, package insert). “Unexpected” also refers to the AEs that are mentioned in the IB as occurring with a class of drugs or as anticipated from the pharmacological properties of the drug, but are not specifically mentioned as occurring with the particular drug under investigation.

For the purposes of this study, each unexpected AE reported by a subject undergoing study treatment or a study-related procedure will be recorded on the AE eCRF.

12.1.1.4 Preexisting Diseases

Preexisting diseases that are present before entry in to the study are described in the medical history, and those that manifest with the same severity, frequency, or duration after IP exposure, will not be recorded as AEs. However, when there is an increase in the severity, duration, or frequency of a preexisting disease, the event must be described on the AE eCRF.

12.1.2 Assessment of Adverse Events

For the purposes of this study, each non-serious untoward medical occurrence reported by a subject undergoing study-related procedure(s) before the first M923 or EU RPP treatment will be recorded on the AE eCRF; however, these events will not be considered as AEs and will not be included in the analysis of AEs.

Each treatment-emergent AE (non-serious AE or SAE) from the first M923 or EU RPP treatment until study completion/discontinuation (Week 48) or 4 weeks following the last M923 or EU RPP treatment (for early termination subjects) will be described on the AE eCRF using the medical diagnosis (preferred), or, if no diagnosis could be established at the time of reporting the AE, a symptom or sign, in standard medical terminology in order to avoid the use of vague, ambiguous, or colloquial expressions (see definition in [Section 12.1](#)). Each AE will be evaluated by the investigator for:

- Seriousness as defined in [Section 12.1.1.1](#)
- Severity as defined in [Section 12.1.2.1](#)

- Causal relationship to IP exposure or study procedure as defined in [Section 12.1.2.2](#)

For each AE, the outcome (ie, recovering/resolving, recovered/resolved, recovered/resolved with sequelae, not recovered/not resolved, fatal, unknown) and if applicable action taken (ie, dose increased, dose not changed, dose reduced, drug interrupted, drug withdrawn, not applicable, or unknown) will also be recorded on the AE eCRF. Recovering/resolving AEs will be followed until resolution, medically stabilized, or 30 days after the study completion/termination visit, whichever comes first. If the severity rating for an ongoing AE changes before the event resolves, the original AE report will be revised (ie, the event will not be reported as separate AE). During the course of any AE, the highest severity rating will be reported.

Deviations from the protocol-specified dosage (including overdosing [any dose that is at least 20% higher than the highest explored dose level], underdosing [any dose that is lower than the intended explored dose level by 10%], abuse, and withdrawal [see [Section 9.3](#)]), treatment errors (including incorrect route of administration, use of an incorrect product, and deviations from the protocol-defined dosing schedule), failures of expected pharmacological actions, and unexpected therapeutic or clinical benefits will be followed with regard to occurrence of AEs, lack of efficacy, and/or other observations because these events may be reportable to regulatory authorities.

Any pregnancy that occurs after administration of M923 or EU RPP will be reported on a Pregnancy Form and followed-up at 1 year post-delivery, if feasible.

If an investigator becomes aware of an SAE occurring in a subject after study completion, the SAE must be reported on the SAE Form **within 24 hours after awareness**; no additional reporting on eCRFs is necessary.

A post-trial SAE report (SAER) form in paper will be used to report SAEs after a subject's completion.

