2. SERIOUS ADVERSE EVENT REPORTING

The investigator will comply with applicable laws/requirements for reporting serious adverse events (SAEs) to the ECs.

Questions pertaining to an SAE should be directed to:

[contact]

ALL SAEs ARE TO BE REPORTED ON THE ELECTRONIC CASE REPORT FORM (eCRF) AND TRANSMITTED TO THE SPONSOR WITHIN 24 HOURS AFTER BECOMING AWARE OF THE EVENT

See eCRF for contact information.

Further details are also available in the study team roster.

For definitions and information on the assessment of these events, refer to the following:

- Adverse events (AE), [Section 12.1](#)
- SAE, [Section 12.1.1.1](#)
- Assessment of AEs, [Section 12.1.2](#)

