10.3.4 Safety Follow-up

At the safety follow-up visit (Visit 20; Safety Follow-up, Week 52 ± 2 weeks), the following assessments will be performed:

- Review of concomitant medications/non-drug therapies
- AE monitoring
- sPGA, PASI, BSA evaluation
- Brief physical examination
- Vital signs (body temperature, pulse rate, blood pressure, and respiratory rate and measure body weight)
- PK and immunogenicity

- Clinical laboratory assessments (hematology and serum chemistry)
- Urinalysis
- Urine pregnancy test (female subjects of childbearing potential only)

The safety follow-up visit is done by subjects who completed the study treatment as per protocol requirements and those who have withdrawn from the study early.

If the subject does not show up to the clinical visit, the site should try contacting the subject by phone for at least 8 weeks after the scheduled follow-up visit and obtain information regarding the occurrence of adverse events, treatments for psoriasis as well as other concomitant medications and pregnancy status. In case the subject is a female of childbearing potential, at Week 48 a urine dipstick pregnancy test should be provided.

Information collected after Week 52 visit will be collected only as source data and not included in the eCRF.

At the safety follow-up visit the investigator should consider the next therapy to prescribe to the subject off-study, in order to maintain clinical benefit.

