The number and percentage of subjects with any AE, any related AE, any severe AE, any related severe AE, any SAE, and any related SAE, as well as the total number of events for each category, will be summarized by treatment group. The number of deaths due to an AE, hospitalization due to an AE and study discontinuation due to an AE will be summarized by treatment arm and analysis period (Arm A and B up to Week 16; Arm A, B1 and B2 after Week 16).

The number and percentage of subjects with an AE, as well as the total number of AEs, will be summarized for each treatment arm and analysis period (Arm A and B up to Week 16; Arm A and B2 after Week 16). This tabulation will be repeated by relationship and severity.

AEs that occurred before first dose of study drug will be listed separately. Any adverse events reported more than 30 days after a subject has completed or withdrawn early from the study, will not be summarized but will be listed.

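### Study completion means Week 48 in some sections and the last visit (Week 52) in others, so an SAE starting between the two may not reach the eCRF or the Follow-up summaries

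*Protocol*

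**What the plan says.** **When eCRF recording ends.** Protocol 12.1.2 has each treatment-emergent AE, serious or not, described on the AE eCRF from the first dose "until study completion/discontinuation (Week 48) or 4 weeks following the last M923 or EU RPP treatment". The second limb applies to subjects who stop early. For an SAE occurring after study completion, the same section requires an SAE form within 24 hours of awareness and adds that "no additional reporting on eCRFs is necessary". It continues: "A post-trial SAE report (SAER) form in paper will be used to report SAEs after a subject's completion".

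**What completion means.** Protocol 10.3.3 and 12.1.2 attach study completion to Week 48. Protocol 8.3 and SAP Section 2 equate subject completion with the last study visit, at the end of the 4-week follow-up. Protocol 10.6 ties completion to having done all study procedures.

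**Other rules on the same events.** Protocol Section 2 sets no time limit: "ALL SAEs ARE TO BE REPORTED ON THE ELECTRONIC CASE REPORT FORM (eCRF"). Protocol 10.3.4 lists AE monitoring at the Week 52 visit and says: "Information collected after Week 52 visit will be collected only as source data and not included in the eCRF".

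**The analysis.** Protocol 13.4.4.2 and SAP 8.1 both plan TEAE summaries with a Follow-up row after Period 4, which ends at Week 48. SAP 8.1 also ends the TEAE window at Week 48 for completers. It lists, but does not summarize, this group: "Any adverse events reported more than 30 days after a subject has completed or withdrawn early from the study".

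**The concern.** A site that follows 12.1.2 with that section's own date would stop required eCRF entry at Week 48 and put a later SAE on paper only. A site that follows Section 2 or 10.3.4 would enter the same SAE on the eCRF. Which events reach the clinical database would then depend on the site.

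The safety of M923 against EU RPP, and of B2 against B1, is judged from summaries of that database. The transition comparison is a stated secondary objective. For Arm B2 the interval follows the last scheduled transition to M923 (Week 37). Serious events are few, so one unrecorded event can be a visible share of an arm's count.

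The literal cut-off also treats subjects unequally. Follow-up on the eCRF after the last dose is shorter for those who complete than for those who stop early.

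**Working it through.** The plan states no figure for this point. The check sets the rules side by side, then works out the timing and an upper bound on size.

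**1. Two readings of completion**

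| | Completion = Week 48 | Completion or eCRF cut-off = Week 52 |
|---|---|---|
| Support | Protocol 10.3.3, 12.1.2 | Protocol 8.3, 10.3.4, 10.6; SAP 2 |
| Route of an SAE starting in Weeks 48 to 52 | Paper form, no eCRF entry required | eCRF |
| Consistent with Protocol Section 2? | No | Yes, to Week 52 |
| Completers' new events available for the Follow-up row? | None required on the eCRF | Yes, but the SAP's TEAE end date excludes them |

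**2. Timing**

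Study day = 7 × week + 1, which matches the schedule (Week 48 = Day 337, Week 52 = Day 365).

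- Last dose, Week 47: 7 × 47 + 1 = Day 330.
- Disputed interval: 365 − 337 = 28 days. With the ± 2 week window for Visit 20 (Days 351 to 379) it is 14 to 42 days.
- eCRF recording after the last dose, completers: 337 − 330 = 7 days on the Week 48 reading; 365 − 330 = 35 days on the Week 52 reading.
- Early leavers: 4 weeks = 28 days in Protocol 12.1.2, and 30 days in the SAP TEAE definition. Their follow-up visit is 5 weeks (35 days) after the last dose (Protocol 10.6), so the 12.1.2 limit falls 7 days before it.
- SAP 30-day rule: if completion is Week 48, the boundary is Day 337 + 30 = 367, just after the Week 52 target. The SAP therefore expects AEs reported at a Week 52 visit held on its target day to be in the data and summarized, although its own TEAE window closes at Day 337 for completers.

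**3. Upper bound on the number of SAEs**

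Inputs: 572 randomized (Protocol 13.5) and up to 129 planned in each of B1 and B2 (Protocol 8.2). The SAE rate is assumed at 2 to 6 per 100 patient-years, because the documents give none. No dropout is assumed.

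- All subjects: 572 × 4/52 = 44 patient-years. 44 × 0.02 = 0.9 and 44 × 0.06 = 2.6 SAEs. Over a full year the same rates give 572 × 0.02 = 11 to 572 × 0.06 = 34.
- Each of B1 and B2: 129 × 4/52 = 9.9 patient-years. 9.9 × 0.02 = 0.2 and 9.9 × 0.06 = 0.6 SAEs. Over Weeks 16 to 48: 129 × 32/52 = 79.4 patient-years, or 1.6 to 4.8 SAEs.
- If the 572 split as planned, each B arm has 572/4 = 143 subjects and 11 patient-years, or 0.2 to 0.7 SAEs.

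These are ceilings. Subjects leave before Week 48, including those without a PASI50 response at Week 25 (Protocol 9.3), and only sites using the Week 48 reading would omit events.

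**The case against.** The strongest reply is that the protocol, read as a whole, points to Week 52. Section 10.3.4 is the most specific text on the follow-up and the eCRF, and the summary of changes shows that Amendment 3 added instructions there. The paper form is called post-trial and is tied to a subject's completion, which 8.3 defines as the last visit. A subject still awaiting Visit 20 is not naturally post-trial. Section 2 and the Follow-up row fit this reading. It is a sound account of what was probably intended, but it does not remove the date that 12.1.2 and 10.3.3 print beside the words study completion. 12.1.2 is the section a site consults for recording AEs.

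A reader might go further than the documents allow and infer that SAEs in Weeks 48 to 52 are certain to be absent from the database and from all tables and listings. That is not supported. It follows from only one of the two readings. Waiving eCRF entry by the site does not mean that paper SAE reports stay out of the clinical database. Protocol 17.2 leaves data handling to a data management plan that is not among the documents, so reconciliation may or may not be planned. The sponsor still receives each SAE within 24 hours of the investigator's awareness.

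Two further points stand. The recording rule is not the only cause: the SAP's Week 48 TEAE end date would drop a completer's later SAE from the TEAE summaries even if it were on the eCRF. And the expected number per B arm is below one, the rule is the same in every arm of a double-blind trial, and SAP Section 8 plans no formal safety test. Systematic bias between arms is therefore not the main worry; incomplete and site-dependent counts are.

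**Conclusion.** The conflict is real and should be corrected. Completion carries two dates four weeks apart. The literal text of 12.1.2 contradicts Protocol Section 2, 10.3.4 and the planned Follow-up row, and SAP 8.1 contradicts itself by planning that row while closing the TEAE window at Week 48 for completers. SAEs with onset in the 28 days from Week 48 to Week 52 may be missing from the clinical database and the Follow-up summaries.

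The likely loss is small: at most about 1 to 3 SAEs overall and 0.2 to 0.6 in each of B1 and B2. This rests on an assumed SAE rate, no dropout, every site using the Week 48 reading and no recovery through reconciliation. The case for acting is less the expected count than the unequal recording, 7 days after the last dose for completers against 28 for early leavers, and the low cost of removing it.

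**What to change.** 1. Use one definition of completion in Protocol 8.3, 10.3.3, 10.6 and 12.1.2 and in SAP Section 2. If Week 48 needs its own name, call it end of treatment.
2. In Protocol 12.1.2, require eCRF entry of every AE and SAE with onset through the safety follow-up visit: Week 52 for completers, the post-discontinuation follow-up visit for early leavers. Limit the paper form to SAEs with later onset, and word Section 2 to match.
3. In SAP 8.1, end the TEAE window at the same visit for both groups, so that these events appear by arm in the Follow-up row. State which date starts the 30-day limit for summarizing late reports.
4. Reconcile all paper SAE forms with the clinical database before final lock, and document it.

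The cost is wording in two documents and one reconciliation step. The Week 52 visit already includes AE monitoring, so no visit or assessment is added. If the wording cannot be changed in time, step 4 alone would recover the SAEs reported on paper, and step 3 is still needed for them to be summarized.
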